4.2 Case screening

According to various examinations, those who meet the inclusion criterias are screened out.

The patients entered the study after completing the required examinations and being evaluated according to the inclusion criterias. Then sign the informed consent form and get treatment.

5. Study Process

Figure 2. flowchart

6. Surgical Technique

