**Single-center, Retrospective Study
of Retro - Auricular Single - Site
Endoscopic, Transoral Endoscopic
Thyroidectomy Vestibular Approach
and Transareola Endoscopic
Thyroidectomy in Patients With
Early Stage Papillary Thyroid
Carcinoma**

Study Protocol

Version date: February 11, 2023

Official Title	Single-center, Retrospective Study of Retro - Auricular Single - Site Endoscopic, Transoral Endoscopic Thyroidectomy Vestibular Approach and Transareola Endoscopic Thyroidectomy in Patients With Early Stage Papillary Thyroid Carcinoma
Brief Summary	The goal of this retrospective study is to compare the safety and efficiency of endoscopic thyroidectomy via retro - auricular single - site approach, transoral endoscopic thyroidectomy vestibular approach and transareola approach.
Conditions	Age: 18 ~ 70 years. Patients with early stage papillary thyroid carcinoma.
Sample Size	160
Inclusion Criteria	
 ● Age 18-70 years old, no gender restrictions. ● Fine-needle aspiration cytology(FNA) confirmed papillary thyroid carcinoma(PTC). ● Early stage PTC (stage T1N0M0). ● Preoperative ultrasonography showed unilateral glandular lobe malignant tumor and the largest diameter was not more than 2cm, without cervical lymph node metastasis and extensive metastasis. ● Patients undergoing thyroid lobectomy and central lymph node dissection. ● Patients who have signed an approved Informed Consent.
Exclusion Criteria	
 ● Patients who do not accept case data collection for various reasons. ● The clinical data unfit this study (at the discretion of the investigator) . ● Patients who have undergone neck surgery or radiotherapy before this trail. ● Patients who have uncontrolled hyperthyroidism.
Elimination Criteria	
 ● Patients who violated the requirements of the research protocol. ● The quality of data records is incomplete and inaccurate. ● Lost cases.
Study Completion	2023-02-28
Locations	1

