Compare the traumatic differences between the three groups by comparing the preoperative and postoperative CRP levels of the three groups.

2.2 Secondary purpose:

Compare the degree of surgical trauma between the three groups by comparing the level of SAA, blood loss, VAS pain score, and postoperative drainage.

Compare the clinicopathologic characteristics between the three groups by comparing the number of resected lymph nodes, and the positive rate of lymph nodes.

Compare the safety between the three groups by comparing the types and rate of complications.

2.3 Primary Outcome Measure:

CRP level

2.4 Secondary Outcome Measures:

- Cosmetic outcome: postoperative cosmetic outcomes
- Surgical outcomes: SAA level, blood loss, VAS pain score, postoperative drainage volume, Operative time.
- Clinicopathologic characteristics: tumor size, number of lymph nodes, the positive rate of lymph nodes.
- Complication: complication rates and types.

3. Study Eligibility

3.1 Inclusion Criteria:

- Age 18-70 years old, no gender restrictions;
- Patient must be suitable candidates for surgery;
- Be able to understand the purpose of the test;
- Preoperative ultrasound showed unilateral glandular lobe malignant tumor and the largest diameter was not more than 2cm, and preoperative imaging examination showed that the largest diameter of central lymph node was not more than 2cm without lateral cervical lymph node metastasis and extensive metastasis;
- Patients who have cosmetic requirements;
- Patients who have signed an approved Informed Consent

3.2 Exclusion Criteria:

- Patients who do not accept case data collection for various reasons.
- The clinical data unfit this study (at the discretion of the investigator) .
- Patients who have undergone neck surgery or radiotherapy before this trail.
- Patients who have uncontrolled hyperthyroidism.

3.3 Withdrawal criteria:

(A withdrawal case refers to a patient who withdraws from treatment for various reasons in study. Patients with the following conditions will be withdrawn from investigational treatment.)

- The patient himself or his legal representative requests to withdraw;
- In the opinion of the investigator, the patient's continued participation in the study will

be detrimental to his health.

3.4 Elimination Criteria:

- Patients who violated the requirements of the research protocol;
- The quality of data records is incomplete and inaccurate.
- Lost cases.

4. Case Screening

4.1 examination items

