All cases must complete the following examination items before being considered for entry into this study. It is generally required to be completed within 7 days before treatment.

- Complete medical history and comprehensive physical examination, including symptoms, signs and specialist examination.
- Check items that must be done before routine treatment, including:

Blood routine: neutrophil/lymphocyte ratio,

Coagulation function: d-dimer,

Serological tests: CRP, SAA, procalcitonin, calcium level,

Thyroid function: TSH level, parathyroid hormone level,

Thyroid ultrasonography and FNA, thyroid Computed tomography scan if necessary,

Chest X-ray, abdominal ultrasonography, electrocardiogram.

The above examinations are all routine preoperative examinations, which do not cause additional financial burden on patients.

[figure not shown]

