8.1 Informed consent

Before each patient was enrolled in this study, the research investigators are responsible for a complete and comprehensive introduction to the surgical method of this study, its possible side effects and possible risks, and let patients know their rights, risks and benefits to be assumed. Patients should have signed informed consent before enrollment.

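### The study is labelled retrospective, but its entry rules describe prospective screening and consent, and no stated operation dates or case-finding rule fix who is analysed

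*Combined protocol and SAP*

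**What the plan says.** The title says retrospective, and the summary repeats it: "The goal of this retrospective study is to compare the safety and efficiency" of three endoscopic approaches. The synopsis gives a sample size of 160 and a completion date of 28 February 2023; the title page reads "Version date: February 11, 2023".

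The entry rules run the other way:

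- Section 4.1: "All cases must complete the following examination items before being considered for entry into this study", generally in the 7 days before treatment.
- Section 4.2: patients enter after being examined and evaluated. The next sentence is "Then sign the informed consent form and get treatment".
- Section 8.1: investigators explain the surgical method and its risks in advance. "Patients should have signed informed consent before enrollment".
- Section 3.1: patients must be fit candidates for an operation and must have signed consent. Signed consent is also an inclusion criterion in the synopsis.
- Section 3.3: a patient may be withdrawn from the investigational treatment.
- Synopsis and Section 3.2: one exclusion is "Patients who have undergone neck surgery or radiotherapy before this trail". Another covers data that the investigator judges unfit.

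**The concern.** A retrospective cohort is defined by a list of operations already done, a date window and criteria applied to the chart. A prospective cohort is defined by screening and consent before treatment. The two definitions can pick out different patients, and this plan uses the label of one with the procedures of the other. The mismatch is more than a matter of style, because signed consent and the prior-surgery exclusion help decide who is analysed.

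If the operations came before the study, CRP (the primary outcome) and the complications were already on file when patients were selected. A plan without a date window or a consecutive-case rule, but with a discretionary exclusion, then allows selection with those results in view. If consent was sought after surgery, willingness or availability to sign could also differ between approaches. A reader could not check either possibility.

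**Working it through.** The question is mainly one of consistency. The plan gives no figure on this point to reproduce.

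**1. Label against procedure**

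| Item | Retrospective cohort | What the plan states |
|---|---|---|
| Status at entry | Already operated on | Candidate for surgery (3.1) |
| Tests | Read from the record | Completed before entry, generally in the 7 days before treatment (4.1) |
| Consent | Data-use consent or a waiver, timing stated | Entry, then consent, then treatment (4.2); consent before enrolment (8.1) |
| Withdrawal | From data use | From treatment (3.3) |
| Source of cases | Operating list, stated dates | Not given in the readable text |

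The exclusion for patients who refuse case data collection does fit a record review. To a degree, so do the criteria on unfit or incomplete data. The other rules in the table are written for patients not yet treated.

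**2. Sections 4.2 and 8.1.** Section 4.2 places study entry before the consent form. Section 8.1 places consent before enrolment. Both orders cannot be the rule.

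**3. Prior-surgery exclusion.** The rule is timed relative to the trial, and the readable text does not say when the trial begins for a given patient. The index operation is lobectomy with central node dissection (synopsis; not repeated in 3.1), which is itself neck surgery. The rule works if it refers to surgery before the index operation, which is probably the intent.

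**4. Room for selection after the results.** Section 3.2 allows exclusion of data at the investigator's discretion. Section 3.4 removes incomplete records and lost cases. Section 1 reports that a retrospective comparison of two of the three approaches has already been published; whether its patients are among the 160 is not stated.

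**5. Dates.** Inputs: version date 11 February 2023 (title page), completion date 28 February 2023 and N = 160 (synopsis).

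- Interval: 28 − 11 = 17 days, or 18 counting both ends.
- Rate if all 160 were enrolled in that interval: 160 / 17 = 9.4 per day; 160 / 18 = 8.9 per day.

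About 9 patients per day at one centre suggests that most operations took place before this version. It does not prove it: no study start date is given, and earlier versions may exist.

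**The case against.** The strongest reply is that this is trial-template wording around a chart review, and that the criteria still work. Much of that stands. Age, cytology, stage, tumour size on preoperative ultrasound, type of operation and thyroid status can all be read from a chart. Section 4.1 itself describes its tests as routine before surgery. A reader might infer that selection rests wholly on unwritten rules, but the documents do not support that.

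A reader might also infer that the prior-surgery exclusion, taken literally, removes every patient. That reading is strained. The synopsis requires the index operation, so it cannot sensibly exclude people for having had it. The wording needs clarifying, but total exclusion is not a measure of impact.

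The 17-day interval might be taken to show that prospective enrolment was impossible. It does not, because a version date is not a start date.

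Nor do the documents show that consent came after the outcomes. Patients might have consented before surgery and been analysed later. The plan does not say so, and such a study would not be purely retrospective.

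Finally, the Section 5 flowchart and another figure are not shown and might carry dates or a case source. The gap is therefore judged on the readable text only.

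What remains is the conflict between label and procedure, the conflict between 4.2 and 8.1, and a discretionary exclusion with no visible date window or case-finding rule beside it.

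**Conclusion.** The point holds in this form: the retrospective label and the entry rules in 3.1, 3.3, 4.1, 4.2 and 8.1 describe different studies, and Sections 4.2 and 8.1 disagree on whether entry or consent comes first. On the readable text, inclusion can be decided after CRP and complications are known, and nothing in the plan would let a reader rule that out. This is a weakness in the plan, not evidence that selective inclusion occurred. It should be corrected, but it does not by itself invalidate the comparison.

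No numerical size can be put on the effect. The documents do not say how many operated patients were passed over, by approach, or why. The one available figure, about 9 patients per day over 17 days, is supporting evidence only and assumes that all 160 were enrolled under this version. The conclusion also assumes that the missing figures do not supply the date window or the source of cases.

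**What to change.** 1. State one design. If it is retrospective, write in Sections 4.2 and 5 that all consecutive patients who had the index lobectomy with central dissection by one of the three approaches, between a stated first and last date, are taken from the operating list. Add that eligibility is judged only on information available before the index operation.
2. In the synopsis and Section 3.2, time the prior neck surgery and radiotherapy exclusion relative to the index operation. This clarifies the probable intent.
3. Reconcile Section 3.3, and the consent statements in the synopsis, 3.1, 4.2 and 8.1, with the stated design and with what the ethics committee approved. If patients consented before surgery and were analysed later, say so and describe the design accordingly.
4. Report, per approach, how many operated patients were left out for lack of consent and how many at the investigator's discretion.

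The cost is protocol wording and one flow count per approach. The operating list is the only additional source needed.

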6.1 Retro-auricular single-site endoscopic thyroidectomy (RASSET)

For the RASSET technique, in the beginning, patient was placed in a supine position with slight neck bending. When the lower pole of the thyroid gland was going to be dissected, the patient was placed in a supine position with slight neck extension. Mark the operation path on the surface. Slit the skin, subcutaneous tissue and superficial cervical fascia in turn. Expose the middle branch of the great auricular nerve and the sternocleidomastoid muscle under direct vision. The working space was created in the superficial layer of deep cervical fascia between the sternocleidomastoid muscle and the platysma muscle, which meets the principle of membrane anatomy. The area of flap dissection just includes the anterior cervical muscle and the anterior edge of the sternocleidomastoid muscle, which is so narrow to minimize the traumatic dissection. Pulling apart the anterior cervical muscle and the sternocleidomastoid muscle along the deep cervical fascia can fully expose the thyroid gland, the recurrent laryngeal nerve (RLN) and common carotid artery that are surrounded by the middle layer of deep cervical fascia and ensure that tumor and central lymph nodes en - bloc resection can be operated in the middle layer of deep cervical fascia to conform the natural anatomical region. For details, please refer to "Retroauricular Single-Site Endoscopic Thyroidectomy—A Balanced Endoscopic Approach for Thyroid Excision".

6.2 Transoral Endoscopic Thyroidectomy Vestibular Approach(TOETVA)

For the TOETVA technique, the patient was placed in a supine position with slight neck extension under nasotracheal intubation. Amoxicillin–clavulanic acid, 1.2 g, was administered 30 minutes before incision. Three laparoscopic ports (a 10-mm port at midline and two 5-mm ports at the lateral junction between the canine and first premolar teeth) were inserted under the lower lip at the oral vestibular area. A standard 10-mm 30° laparoscope was used, allowing top-down visualization. The working space was created down to the sternal notch with the lateral border at the sternocleidomastoid muscles. The strap muscles were separated in the midline and retracted laterally by a transcutaneous 2/0 silk suture to expose the thyroid and trachea. The thyroid isthmus was divided first. Next, the superior pole was dissected, and the branches of the upper pole vessels were divided using ultrasonic shears (Harmonic Scalpel) on the surface of the thyroid gland. Upper parathyroid and lower parathyroid glands were identified and preserved. The recurrent laryngeal nerve (RLN) was identified at the insertion to the larynx, then followed down and parallel to the trachea inferiorly. A thyroid lobe specimen was placed in a specimen pouch and retrieved through the 10- to 15-mm central incision.

6.3 Transareola Endoscopic Thyroidectomy

After endotracheal intubation and general anesthesia, the patient was placed in supine position. Incision was made inside the right areola and a 10-mm port was placed, subcutaneous tunnel separation rod was used to separate the space, and a 30° laparoscope was introduced, a 5-mm port was placed in the 5mm incision in the left areola, free flap with ultrasonic shears, and subcutaneous separation space in the upper sternal segment. A 5-mm port was placed on the lateral side of the right areola, and the anterior cervical flap was further dissociated to establish space. Above the flap was the thyroid cartilage and behind the sternocleidomastoid muscle on both sides, the median cervical line was cut, the isthmus of the thyroid was cut off, and the tracheal fascia ligament of the thyroid was separated on both sides, and the lower pole blood vessel and the lateral middle vein were treated close to the gland, and the inferior parathyroid gland was exposed. The

recurrent laryngeal nerve was exposed in the parathyroid groove at the lower pole of the gland, the space along the nerve was separated to protect the nerve and protect the superior parathyroid gland, the suspensory ligament was cut off, the upper pole blood vessels were treated close to the upper pole glands, and the affected lobe glands were excised.

7. Outcome Measures

7.1 Baseline Characteristics of Patients

Gender, Age, BMI, Tumor size, Pathological type, Tumor location, ASA grade.

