Thyroid cancer is one of the most common malignant tumors in the head and neck. Among it, papillary thyroid carcinoma accounts for about 70% of thyroid cancer. The degree of malignancy is low, but there is a tendency for multicentricity, and cervical lymph node metastasis occurs early. Due to the development of diagnosis technology, the amount of papillary microcarcinoma is getting higher and higher. At the same time, the change of aesthetic makes young women pursue a scarless neck^{1, 2}. Surgery is the first choice of treatments for early-stage thyroid cancer.^{3, 4} Traditional open surgery tended to leave a long scar on the neck, which affects the cosmetic outcome. At present, many reported approaches, such as trans-areola approach⁵, trans-axillary approach⁶, trans-oral approach^{7, 8} or some combined approaches⁹, all have wider flap dissection or greater body trauma, and at the same time, these above approaches are difficult to achieve complete dissection of central lymph nodes¹⁰. Therefore, based on the experience of transauricular hairline endoscopic thyroidectomy¹¹⁻¹³, we established a new operative method-the Retro-auricular single-site endoscopic thyroidectomy (RASSET). The incision is only 3cm and located at the posterior sulcus of the auricle, which can meet the cosmetic needs. Compared with other endoscopic approaches, the dissection area is small and the flap dissection is small, which may reduce the surgical trauma. The RASSET is easy to resect the upper pole of the thyroid gland, and can achieve complete dissection of the central lymph nodes. The article titled "A comparative study between retro - auricular single - site endoscopic thyroidectomy and transoral endoscopic thyroidectomy vestibular approach: a single - center retrospective analysis" has been published in "Chin J Surg"¹⁴. Guangdong Medical Information Research Institute recognized that there was no report of endoscopic thyroid surgery for this approach at home and abroad, and it also passed the new technology evaluation in the Sun Yat-sen University Cancer Center, and was recognized as an international leader.

Figure 1. A:Sun Yat-sen University Cancer Center Certificates(international innovation). **B:**Guangdong Medical Information Research Institute Certificates(no report of this approach). **C:**Zhonghua Wai Ke Za Zhi(a new approach).

2. Study purpose

2.1 Primary purpose:

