7.2 Postoperative Outcomes

- Surgical outcomes: CRP level, SAA level, Drainage volume, intraoperative blood loss, VAS pain score, Operative time.
- Clinicopathologic characteristics: tumor size, number of lymph nodes, the positive rate of lymph nodes.
- Complications: complication rates and types.

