10.3 Storage of data

The researcher should keep the data intact. According to the principle of GCP in China, for the investigators or hospitals, the data storage should be more than 5 years.

11. Statistical analysis

Professional statisticians undertake statistical analysis tasks and participate in the whole process from experimental design, implementation to analysis and summary. After the study protocol and case report form are completed, a statistical analysis plan shall be formulated. After some necessary modifications shall be made during the study process as required, and a statistical analysis report shall be provided after the data analysis is completed.

All analyses were performed using SPSS 26.0, and a P value less than 0.05 was considered significant. Normally distributed quantitative data are represented by mean (SD) [range]. Non-normally distributed quantitative data are represented by M (QR) . Comparison between groups was performed using the Mann-Whitney U test. Categorical data are expressed as frequencies and percentages. Comparisons between groups were performed using the χ^2 test or Fisher's exact test.

References:

2. Choi JY, Lee KE, Chung KW, et al. Endoscopic thyroidectomy via bilateral axillo-breast

- approach (BABA): review of 512 cases in a single institute. *Surg Endosc.* 2012;26(4):948-955.
 5. Sephton BM. Extracervical Approaches to Thyroid Surgery: Evolution and Review. *Minim Invasive Surg.* 2019;2019:5961690.

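### Operating surgeon and operation date are neither named nor analysed, so a difference between approaches in CRP, blood loss or operative time could reflect who operated or when

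*Combined protocol and SAP*

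**What the plan says.** The synopsis describes a retrospective comparison: "The goal of this retrospective study is to compare the safety and efficiency of endoscopic thyroidectomy via retro - auricular single - site approach", set against the transoral and transareola approaches. No allocation rule is described. The total is 160 patients, with no split by group. No inclusion window is given, only a study completion date of 2023-02-28.

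The Background (Section 1) says of the first approach: "we established a new operative method-the Retro-auricular single-site endoscopic thyroidectomy (RASSET". It adds that the method passed a new-technology evaluation at the centre. Nothing comparable is said of the other two approaches.

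The primary purpose (Section 2.1) is "Compare the traumatic differences between the three groups by comparing the preoperative and postoperative CRP levels of the three groups". Section 7.2 lists the surgical outcomes as "CRP level, SAA level, Drainage volume, intraoperative blood loss, VAS pain score, Operative time".

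Section 7.1 gives the baseline variables: "Gender, Age, BMI, Tumor size, Pathological type, Tumor location, ASA grade". Section 4.1 adds preoperative tests. Neither section, nor any other, names the operating surgeon, the date or period of operation, or the surgeon's case order.

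For quantitative outcomes, Section 11 says: "Comparison between groups was performed using the Mann-Whitney U test". For categorical ones: "Comparisons between groups were performed using the χ^2 test or Fisher's exact test". It has no covariate, stratum or model.

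**The concern.** When treatment is not randomised, the choice of approach can follow the surgeon and the date. Here the documents give a specific reason to ask about both, because one of the three approaches is described as new to the group running the study. Its cases could differ from the others in the surgeon's experience with the technique, in calendar period, or in who operated.

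The outcomes are plausibly sensitive to those factors. The plan reads CRP as a measure of surgical trauma, and blood loss, drainage and operative time all depend on how the operation is carried out. If surgeon or period differs by approach, the planned tests credit the whole difference to the approach, and the primary conclusion carries that error.

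This is distinct from the general point that the tests are unadjusted. A regression on all seven variables in Section 7.1 would still leave surgeon and period untouched, because neither is on the list. The plan also gives readers no way to see whether surgeons and periods overlap across approaches.

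**Working it through.** **1. Is the omission real?** Sections 2.3, 2.4, 4.1, 7.1, 7.2 and 11 and the synopsis were read for surgeon, number of surgeons, operation date, period, case order and adjustment. None appears. The seven items in Section 7.1 are all patient or tumour features.

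**2. Is there a figure in the plan to reproduce?** No. The total of 160 comes without an effect size, SD, power or group split. The figures below are therefore illustrations, and their assumptions are labelled.

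**3. What would a shift do to the planned test?** Assumptions:
- about 53 per group (160/3 = 53.3; the equal split is assumed);
- two-sided 0.05 (the plan gives 0.05 but not the sidedness);
- no true approach effect;
- a difference of d SD between two groups that is due only to surgeon or period.

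The noncentrality is d × √(53/2) = d × 5.148. The chance of P<0.05 is Φ(noncentrality − 1.96) + Φ(−noncentrality − 1.96).

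| Shift d (assumed) | Noncentrality | Chance of P<0.05, normal approximation | Mann-Whitney simulation, 4,000 runs |
|---|---|---|---|
| 0 | 0 | 5.0% | 5.6% |
| 0.2 | 1.03 | 17.7% | 16.6% |
| 0.3 | 1.54 | 33.9% | 32.5% |
| 0.5 | 2.57 | 73.0% | 70.6% |

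These rates are for one pairwise comparison.

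**4. What would adjustment cost?** Let R² be the share of the variation in approach explained by surgeon and date. With residual variance held fixed, the standard error grows by 1/√(1 − R²). The difference detectable with 80% power in one pairwise comparison is (1.960 + 0.842) × √(2/(53 × (1 − R²))).

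| R² (assumed) | Standard-error multiplier | Detectable difference |
|---|---|---|
| 0 | 1.00 | 0.54 SD |
| 0.25 | 1.15 | 0.63 SD |
| 0.50 | 1.41 | 0.77 SD |
| 0.75 | 2.00 | 1.09 SD |

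At R² = 1, where each approach has its own surgeon or its own period, no model can separate the two.

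**The case against.** The strongest reply is that the documents show no imbalance. A reader might infer from the newness of RASSET that its cases come from a later period and from the start of a learning curve. No section says so. The Background states that RASSET grew out of earlier experience with a related hairline approach. It also says that a single-centre comparison of RASSET with the transoral approach had already been published, and the reference list dates that report to 2021. RASSET cases therefore existed well before this February 2023 protocol, and the periods may overlap. This part of the reply stands: later period and early experience are possibilities only. It does not remove the point, because the sampled cases could still include early ones, and overlap is what would make adjustment workable.

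A reader might also infer that Section 7.1 is a closed list and that the data will not be collected. That cannot be known. The section is headed as patient characteristics, Section 4.1 requires tests absent from it, the case report form is not included, and the flowchart is not shown. What can be said is that the plan does not name these variables and that no specified analysis uses them.

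It may be tempting to conclude that the effects can never be separated. Section 9 requires original medical records to be kept, and these may well supply surgeon and date, so the gap may be repairable.

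Finally, the size of any shift is assumed. That is right: the table shows what a shift would do, and says nothing about how likely one is.

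**Conclusion.** The point holds in a limited form. In a non-randomised comparison that includes an approach described as new, the plan names neither operating surgeon nor operation date and analyses neither. If these differ by approach, a difference in CRP, blood loss or operative time could reflect them instead of the approach, and the plan as written would not reveal it. The direction is open: limited experience could make RASSET look worse, while a more experienced surgeon or a later period could make it look better.

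Under the stated assumptions, even a modest shift of 0.3 SD raises the false-positive rate of a pairwise comparison from 5% to about 34%. The documents contain nothing from which to estimate the real shift. They do not support a claim that the groups are in fact imbalanced, or that the resulting comparison is biased in a known direction. This should be addressed before the results are interpreted, but it may not be fully removable.

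**What to change.** 1. Add operating surgeon and operation date to Section 7.1, with the surgeon's case order for each approach where the centre's surgical log allows it. Case order must be derived from the surgeon's full series, which may include patients outside the 160.
2. Tabulate approach by surgeon and by calendar period.
3. In Section 11, keep the planned unadjusted tests. Beside them, specify a regression of postoperative CRP (log or rank scale if skewed) on approach, preoperative CRP and operation date, plus surgeon where surgeons performed more than one approach. Section 11 has no model at present, so this has to be written out in full; adding fields to Section 7.1 alone changes no result. Do the same for blood loss and operative time, without the preoperative CRP term.
4. Add a sensitivity analysis limited to the calendar period in which all three approaches were in use.
5. If surgeon or period coincides with approach, word the conclusion as a comparison of approach together with surgeon or period.

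The cost is light chart extraction, with no new patient contact, and some precision. The precision loss is small only if overlap is good: the standard error is about 15% larger at R² = 0.25, 41% larger at 0.50 and doubled at 0.75. For that reason the adjusted result is best reported beside the unadjusted one and not in its place.
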